5. STUDY DESIGN

This study will be conducted as a prospective, randomized pilot study in patients with acute myocardial infarction which have undergone coronary angiography with two study groups (Figure 1):

- **Group 1 (control group):** standard clinical practice medical therapy at discharge, including double antiplatelet therapy (DAPT), high potency statins and if indicated, beta blockers.
- **Group 2 (intervention group):** standard clinical practice medical therapy as above plus the Smarheart home-telemonitoring 12 lead ECG device.

Figure 1: Trial outline

Patients will be randomized at discharge to standard medical therapy (DAPT, high potency statins and beta blockers) or the standard medical therapy plus the Smartheart home-telemonitoring 12 lead ECG device. The intervention group will have instructions and explanation, prior discharge, how to use the device and will be guided to have two device testing's at home during the first two weeks after discharge. In case of any symptoms, including but not limited to chest pain, shortness of breath, sensation of irregular heart beats and near fainting during the 90 days post discharge the patient will record a 12 lead ECG at home and transmit it directly to Saint Mary's Hospital CICU designated study NP/PA, which is available 24/7, the ECG will be read by the NP/PA (with the support of the CICU consultant). Communication with the patient will be through the study designated CICU NP/PA, which will call the participant, record short history of the medical emergency and provide the patient with appropriate directions according to the ECG finding, medical urgency and study protocol. The CICU NP/PA will call the patient as soon as possible after receiving the ECG to the study email inbox.

In case of delay with conducting the phone call to the participant, >15 minutes from sending the ECG, or having any technical issues with recording the ECG, the participant will call to a study phone (number provided to the participant) carried by CICU NP/PA which is available 24/7. An alternative phone number will also be provided that will get the patient in touch with the Mayo Clinic operator who can then direct the patient to the Cardiac Intensive Care Unit (CICU) NP/PA staff. Patients will be instructed to use this if they are unable to reach the NP/PA staff directly with the previously provided phone number. In case the technical issue was not solved by the NP/PA, the recommendation for the patient will be based on the symptoms characteristics (as described in the NP/PA decision making tool). In case the participant cannot be reached by the primary phone number provided, NP/PA will call second provided phone number (of patients' related individual/significant other), in case there is no response to both phone numbers, and the participant did not call our NP/PA designated phone, further decisions will be based on the ECG tracing. If alarming findings are present, which may explain a loss of consciousness, EMS will be activated to the home address of the patient, assuming that patients will use the ECG device at home. If no alarming finding is present the patient will be reassured with a phone follow-up the next day.

Adverse Event Reporting

We will only be collecting adverse events that result in Cardiovascular Events, Emergency Department visits, and Hospitalizations, which will be looking at the outcomes, as this is a monitoring study, with no adverse events expected from the device (SmartHeart, which is FDA approved), as all other events are not relevant to the research study. To make sure assessments are consistent throughout the study, this will also be followed retrospectively.

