Number of Subjects	240 patients in total, enrolled over one-two years

Inclusion and Exclusion Criteria	
Inclusion criteria:
 
 • ≥18 years of age, • Acute myocardial infarction, both STEMI and non-STEMI • Able to use the home ECG telemonitoring • Must have smartphone device with home wi-fi/mobile internet which allows 24/7 ability to transmit ECG • Caring family member who will be able to help/perform the ECG in case the patient himself won't be able to do it • Planned to be discharged home by the treating team 
Exclusion criteria:
 
 • No ability to use the device at home • No smartphone device or home wi-fi/mobile internet which prevent 24/7 ability to transmit ECG • Cannot download the smartheart app • No support in home environment • Out of hospital cardiac arrest: secondary to a non-shockable rhythm, unrelated to an acute coronary syndrome, or with any level of neurologic damage. • Resident of nursing home or acute care facility • Uninterpretable ECG at discharge – left bundle branch block (LBBB), pacemaker or implantable cardioverter defibrillator (ICD) with pacing dependence. • Patients who are planned for staged PCI after the index hospitalization
Study Product, Dose, Route, Regimen	Prior to discharge patients will be 1:1 randomized to standard medical therapy or standard medical therapy + 12 lead ECG Smartheart telemonitoring device.
Duration of Administration	Patients will receive the device for the period of 90 (+/-7) days .
Reference therapy	Group 1 will serve as the reference group
Statistical Methodology	Inter-group differences in the rates of the primary combined endpoint will be analyzed by the Chi square test.

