6. SELECTION AND ENROLLMENT OF PARTICIPANTS

6.1 Inclusion Criteria

- ≥18 years of age,
- Acute myocardial infarction, STEMI and NSTEMI
- Ability to use the device at home
- Must have smartphone device with home wi-fi/mobile internet which allow 24/7 ability to transmit ECG
- Caring family member who will be able to perform the ECG in case the patient himself won't be able to do it

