7. STUDY INTERVENTIONS

Interventions, Administration, and Duration

Patients will be randomized to either standard medical therapy or standard medical therapy + Smartheart home telemonitoring device. The device will be supplied by the "SHL" telemedicine for each patient in the intervention group for the period of 90 (+/-7) days from the randomization. Patients will be followed for 90 (+/-7) days. At randomization and at the end of the study period the patients will be asked to fill out quality of life questionnaire and return back the Smartheart device by mailing back the device in the padded box covered by

[figure not shown]

Figure 2. Call work-flow

insurance in case it is damaged upon receipt to Mayo Clinic. Medications during the study period will be prescribed by the treating physician, no change of medications will be performed by the study team.

The SmartHeart, developed by SHL Telemedicine Ltd., was approved by the FDA on 2012 (K113514). It is a personal, hand-held device, enabling an individual to immediately transmit a 12-lead ECG from anywhere and anytime, using a smart phone application, to a physician's office, hospital or monitoring center. The ECG output from Smartheart device was compared to standard 12 lead ECG recordings and was found to be reliable. Data will be labeled with a subject's medical record number and by date of transmission. The data will be uploaded from Smartheart device to the US cloud (located in USA), and sent by email directly to designated Mayo Clinic CICU NP/PA smartphone devices email address. The smartphone device will be carried by the NP/PA 24/7 and will give a loud alert for every incoming ECG. The ECG data will be uploaded and accessible in the patient's EPIC EMR.

The smart phone application will send push notifications to the patients to remind them to perform test ECG at Week 1, Week 2, and Week 4 (optional, if patient has not performed Week 2 ECG). Patients will also be notified every other day after Week 1, if not completed.

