9.4. Interim Analyses and Stopping Rules

Due to the uncertainty in proposed rehospitalization rate of the treatment arm, a sample size reestimation (SSR) will be performed after 60 patients have finished the study in the treatment group. The rate will be estimated only for the treatment group, and the sample size will be recalculated using the new calculated rate. The results of this calculation will be the new larger sample size for the study. If the calculation proposes a sample size that is smaller, the original 120 patients per group will be used. No stopping rules are implemented for this pilot study.

As an example, there may be more rehospitalizations and ER visits than expected in the treatment group. If the rehospitalizations and ER visits were 17.5% at 90 days, this would result in the sample size being increased to 181/group. Alternatively, if the rehospitalizations and ER visits in the treatment group were 10%, the sample size required would only be 62/group. If this were to happen, the sample size for the study would be maintained at 120 per group.

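### When nobody can be reached and the tracing is alarming, EMS is sent to the home address on an assumption of home use; a dated temporary address on file would be a cheap, minor safety improvement

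*Combined protocol and SAP*

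**What the plan says.** Section 5 (Study Design) sets out what happens after a device-arm patient transmits an ECG. The NP/PA calls the patient and, failing that, a second contact. The patient is told to ring a study phone if no call comes within 15 minutes, and has an operator number as backup. The branch at issue begins "in case there is no response to both phone numbers, and the participant did not call our NP/PA designated phone". The decision then rests on the tracing alone. If it shows findings that could account for the patient being unconscious, the instruction is: "EMS will be activated to the home address of the patient, assuming that patients will use the ECG device at home". No other address is mentioned.

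On the place of recording, Section 5 says that with any symptom "the patient will record a 12 lead ECG at home and transmit it directly". Sections 6.1 and 6.2 require the ability to use the device at home and exclude patients without support there. Section 7 (Study Interventions) describes the device as "enabling an individual to immediately transmit a 12-lead ECG from anywhere and anytime, using a smart phone application". The connectivity criterion in Section 1 reads "Must have smartphone device with home wi-fi/mobile internet which allows 24/7 ability to transmit ECG", and Section 6.1 has nearly the same wording. Section 7 says the transmitted data are labeled with the "medical record number and by date of transmission".

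**The concern.** The dispatch rule states its own assumption, and the same protocol describes a device and a connectivity requirement under which that assumption need not hold. In every other branch, someone who answers the phone can say where the patient is. Here each of those contacts has failed by definition, and the tracing suggests a patient who may be unconscious. If the ECG was recorded at a relative's house or on a trip, following the rule as written would send EMS to the wrong place. Section 4.2 states the intent that, for STEMI, VT/VF or complete AV block, EMS goes to the participant. The Section 5 rule meets that intent only if the participant is at home.

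What is at stake is the safety of individual patients in the device arm. Nothing in the analysis depends on it.

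**Working it through.** The plan gives no figure to reproduce, so the check is mainly a reading of the relevant sections against each other.

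1. **Trigger (Section 5).** Three conditions must hold together: no answer on either number, no call from the patient, and an alarming tracing.
2. **Action (Section 5).** EMS goes to the home address, on a stated assumption of home use, with no exception.
3. **Expected place of recording (Sections 5, 6.1, 6.2).** Home. None of the text available bars recording elsewhere.
4. **Is recording elsewhere feasible?** Yes. The device is hand-held and can transmit from any place (Section 7), and mobile internet satisfies the connectivity criterion (Sections 1 and 6.1).
5. **Could the NP/PA learn the location in this branch?** Not from anything described in the text. The labels named in Section 7 are the record number and transmission date. The explanation to patients in Section 8.1.2 covers how the device works, its placement on the chest and transmission. The telephone history does not take place in this branch.
6. **What cannot be read.** Figure 2 (the call work-flow) is not shown, and the NP/PA decision making tool cited in Section 5 is not in the supplied text. Either could contain a location step.

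**Illustrative size.** Expected misdirected dispatches = N × p × a, where:
- N is the number of device-arm patients: 120 (Section 9.2), or 181 in the Section 9.4 re-estimation example ("this would result in the sample size being increased to 181/group");
- p is the share of patients who reach this branch over 90 days. **Assumed**, 0.1% to 2%;
- a is the share of those recordings made away from home. **Assumed**, 5% to 20%.

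| N | Low: p = 0.001, a = 0.05 | Middle: p = 0.005, a = 0.10 | High: p = 0.02, a = 0.20 |
|---|---|---|---|
| 120 | 0.006 | 0.06 | 0.48 |
| 181 | 0.009 | 0.09 | 0.72 |

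The range is 80-fold (0.48 / 0.006 = 80), which shows how little is known. To expect one such event among 120 patients, p × a would have to reach 1/120 = 0.83%. With a = 20%, that means p of about 4.2% (0.0083 / 0.20), roughly twice the top of the assumed range.

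**The case against.** The strongest reply is that the plan already prescribes home recording. The intervention is called home telemonitoring, symptom ECGs are to be taken at home, and home use and home support are conditions of entry. The home address is then a disclosed last-resort default after two outgoing calls and two numbers the patient can ring. The wording about transmitting from anywhere sits in a general product description. The connectivity criterion is also consistent with mobile data used at home, and the labels in Section 7 need not be everything the NP/PA can see. Most of this stands. It makes home the right default and the event rare. It does not remove the possibility: the protocol itself has to assume home use, and the text available neither forbids recording elsewhere nor provides another address.

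A reader might go further and infer that the trial has no means of locating a patient who is away from home. The documents do not support that, because the call work-flow figure and the decision tool are exactly where such a step would sit, and neither can be read here.

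A reader might also want patients to report their location with or after every recording. That would do little in this branch. A patient who rings in has already left it, and no channel for sending a location with the ECG is described.

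Finally, it is fair to say that the calculation adds no evidence on frequency. Both probabilities are assumptions, and the case rests on the possible consequence and the small cost of the change.

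**Conclusion.** The point holds as a minor patient-safety improvement. In one narrow branch, Section 5 directs EMS to an address that may be wrong, on an assumption that the device description and connectivity criterion show can fail. The frequency is unknown and probably very low: fewer than one expected event in the whole trial at every combination of the assumed inputs, up to 0.48 with 120 device-arm patients and 0.72 with 181. The consequence of a single event could be serious.

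The conclusion assumes that the unreadable workflow material does not already supply an alternative address. If it does, only a cross-reference is needed. It would be wrong to read this as a finding that patients are expected to record away from home, or as a threat to the trial's inference. The endpoints, test, power and sample size are untouched.

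**What to change.** At the pre-discharge explanation in Section 8.1.2, ask device-arm patients to give the study phone any temporary address, with start and end dates, before staying away from home. Amend Section 5 so that in this branch EMS goes to the temporary address on file if it is current, and otherwise to the home address. If Figure 2 or the NP/PA decision making tool already does this, cross-refer to it in Section 5 instead.

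The cost is one patient instruction, one sentence in Section 5 and the NP/PA workflow, and one more item to keep current for up to 120 patients (181 in the re-estimation example). No change to the app or device is needed, and the phone triage under test stays as it is. There are two limits. An outdated temporary address could itself misdirect EMS, which is why the end date is needed. Unplanned short outings, such as work or shopping, remain uncovered.

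### When a non-alarming ECG has arrived and nobody can be reached, the visible text of Section 5 provides only a next-day call: add same-day repeat calls, or align the sentence with the call work-flow if it already has them

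*Combined protocol and SAP*

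**What the plan says.** Device patients are told to send an ECG on feeling unwell: "In case of any symptoms, including but not limited to chest pain, shortness of breath, sensation of irregular heart beats and near fainting" (Section 5, Study Design). On receipt the CICU NP/PA rings as soon as possible; this is the person "which will call the participant, record short history of the medical emergency and provide the patient with appropriate directions". If more than 15 minutes pass without a call, the participant is to ring the study phone, and there is a further fallback: "An alternative phone number will also be provided that will get the patient in touch with the Mayo Clinic operator".

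If the participant's own number fails, the NP/PA tries a second number, that of a relative or significant other. The branch at issue opens "in case there is no response to both phone numbers, and the participant did not call our NP/PA designated phone". Decisions then rest on the tracing. Alarming findings send EMS to the home address. Otherwise: "If no alarming finding is present the patient will be reassured with a phone follow-up the next day".

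Section 4.2 (Study Rationale) sets two conditions for advising a patient to put off seeking care: the ECG is reassuring, and suspicion of an acute cardiac event is low.

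Section 7 (Study Interventions) says transmissions are labelled by "medical record number and by date of transmission". It also says the study smartphone "will be carried by the NP/PA 24/7 and will give a loud alert for every incoming ECG".

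**The concern.** The next-day step applies although nobody has been spoken to. The history that Section 5 expects has not been taken, and of the two conditions in Section 4.2 only the one about the tracing can be assessed. The sender may have had chest pain, breathlessness, irregular beats or near fainting within 90 days of an infarct. If the sentence is followed as written, the study makes no further attempt that day.

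What is at stake is the timing of history and advice for a small number of unreached patients. It is a participant-safety and procedure point. It touches neither the primary endpoint analysis nor the error rates.

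**Working it through.** The plan gives no figure to reproduce. The check is a trace of the branch, followed by the sizes that bear on the fix.

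**Tracing the branch (Section 5).**
1. ECG received; NP/PA calls the participant: no answer.
2. NP/PA calls the second number: no answer.
3. No incoming call on the study phone.
4. Tracing not alarming, so EMS is not sent.
5. Only remaining stated action: a phone call the next day.

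No repeat call between steps 2 and 5 appears in the visible text. The other safeguards, the study phone and the operator line, depend on the participant acting.

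**Length of the gap.** With sending time s and next-day calling time c, in hours after midnight, the delay is (24 + c) − s.
- s and c anywhere in the day: more than 0 and less than 48 hours.
- Calls made 08:00-17:00 (assumption): from 24 + 8 − 24 = 8 hours to 24 + 17 − 0 = 41 hours. The upper end needs an ECG sent just after midnight and a call at 17:00 on the following day.

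**When a test could be mistaken for a symptom ECG.** Section 8.1 gives windows of −3 to +6 days. Reading Week n as day 7n (assumption):
- Week 1: days 4-13. Week 2: days 11-20. Together days 4-20 = 17 days; 17/90 = 18.9%.
- Week 4: days 25-34 = 10 days. With it, 27/90 = 30.0%.

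On the other 63 to 73 days, timing alone points to a symptom ECG.

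**Number of scheduled tests.** Section 7 describes the third test as "Week 4 (optional, if patient has not performed Week 2 ECG", which implies two tests per patient. Section 8.1 makes Week 4 depend on a need for training beyond the first two tests, so three are possible. Section 9.4 gives 181 per group as an example after re-estimation. The share of tests ending in failed contact is not in the documents; 5-20% is an assumption.

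| Device patients | 2 tests each | 3 tests each | 5% of lower | 20% of upper |
|---|---|---|---|---|
| 120 | 240 | 360 | 12 | 72 |
| 181 | 362 | 543 | about 18 | about 109 |

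These are upper-side figures for retries, because tests known to be tests are exempt and alarming tracings go to EMS.

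**Calls per episode under the proposed schedule.** Over 4 hours, hourly calls make 4 rounds × 2 numbers = 8 calls; half-hourly calls make 8 rounds × 2 = 16 calls, if no round succeeds. For tests at 120 device patients the range is 12 × 8 = 96 to 72 × 16 = 1,152 calls over the trial. Retries for symptom ECGs come on top and cannot be counted, because the plan gives no expected number of such ECGs.

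**The case against.** **Unseen material.** Figure 2 is the call work-flow and is not shown; the decision tool is cited without its content. A retry step could well sit in either. This stands, and it limits the point to confirming or adding a retry. A reader might infer that the trial has no retry at all, or that it forbids one. The documents support neither: part of the procedure cannot be seen, and the sentence names a next-day call without ruling out earlier attempts. But the sentence is a written instruction, and as it reads the next contact is the next day.

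**Wording.** The reassurance can be read as something the next-day call delivers, not as something already done. That is a fair reading, and the point does not depend on the word.

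**Existing layers.** The second contact, the study phone, the operator line, the required family member (Section 6.1), the exclusion of patients without home support (Section 6.2) and EMS for alarming tracings all make the branch rare. This stands. They do not say what to do once the branch is reached.

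**Reason for the ECG.** A reader might infer that staff normally cannot tell a test from a symptom ECG. That goes too far. The windows cover about 19-30% of days, Section 8.1 pairs the tests with a training call, Section 10.3.4 has patients phoned for device testing, and Section 7 has repeat notifications when a test is not completed, which suggests completion is tracked. The uncertainty lies mainly inside the test windows.

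**Burden.** The added load is not trivial under the less favourable assumptions, and some calls would disturb patients or relatives at night for what proves to be a test. This stands as a cost.

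**Conclusion.** The point holds as a low-cost improvement to one sentence. In the visible text, an unreached sender with a non-alarming tracing gets no further study-side contact until the next day, before any history is taken and with clinical suspicion unjudged. Same-day repeat calls would bring contact forward on a line that is already staffed. If Figure 2 or the decision tool already requires retries, what remains is a mismatch in the text.

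The size of the gap in hours rests on assumed sending and calling times. The 12-72 test episodes (up to about 109 at 181 per group) rest on the assumed 5-20% and on two to three tests per patient. A reader might go on to infer that patients will be harmed; the documents give no frequency of symptom ECGs or failed contacts, so no such count can be made. Power, alpha and sample size do not change.

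**What to change.** Check Figure 2 and the NP/PA decision tool. If they contain a retry, bring the sentence in Section 5 into line with them. If not, replace it with wording such as:

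> If no alarming finding is present, the NP/PA will repeat calls to both numbers at a fixed interval (for example every 30-60 minutes for up to 4 hours), unless the ECG is known to be a scheduled test. An ECG of unknown reason is treated as symptom-triggered. If contact still fails, the NP/PA will call the next day to take a history and advise.

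The study team should set the interval and end point, so that the step is the same on every shift. A test may be known as such because it was arranged on a device-testing call. No new labelling of transmissions is needed, since an unknown reason leads to retries.

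Cost: an amendment to one sentence, matching text in Figure 2 and the tool, and the extra calls sized above, some at night. No additional staffing is foreseen.
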